# 6. STUDY DATA COLLECTION

# 6.1. Study Schematic

The study Time and Event Schedule is presented in Appendix A.

### **6.2.** Data Collection

Data collected from all study procedures and assessments will be collected and documented on the appropriate electronic Case Report Form (eCRF) for the study.

# 6.3. Subject Enrollment

All subjects screened for the study who sign a consent form will be assigned a 5-digit Screening number which will be entered in the Screening and Enrollment Log. Screening numbers will be assigned in sequential order beginning with SXX001 where XX is a 2-digit site number.

Once a subject meets all qualification criteria, they will be randomly assigned to masked treatment using a 1:1 (OTX-DP: PV) assignment ratio. Subjects will be randomized on Visit 4b (Day 1) by assignment of the lowest 4-digit randomization number available at the investigative site, starting with RXX01, where XX is a 2-digit site number. No product numbers will be skipped or omitted. The investigational product will be inserted per the procedures outlined in Appendix G.

# 6.4. Masking

The Sponsor, Investigator and the subject will be masked to the treatment assignment throughout the subject's participation in the study. OTX-DP and PV are identical in appearance and will be supplied in identical packages so they cannot be distinguished by the user. If it is medically necessary to identify the product used, the Investigator will follow procedures outlined in Section 9.9.2.

### **6.5.** Data Collection

Data collected from all study procedures and assessments will be collected and documented on the appropriate electronic Case Report Form (eCRF) for the study.

### 7. STUDY OBSERVATIONS AND PROCEDURES

# 7.1. Subject Screening and Informed Consent

Prior to a subject's participation in the study (i.e., changes in a subject's medical treatment and/or study related procedures), the study will be discussed with each subject, and subjects wishing to participate must give written informed consent using an informed consent form (ICF). The ICF must be the most recent version that has received approval/favorable review by a properly constituted Institutional Review Board (IRB)/Independent Ethics Committee (IEC).

Failure to obtain a signed ICF renders the subject ineligible for the study. Subjects must be willing to remain in the clinic for all CAC titrations and procedures and be willing to return to the clinic for study Visits 2, 3a, 3b, 4a, 4b, 5, 6a, 6b, 7, 8a, 8b, and 9, as required.

Prior to the completion of the Screening Phase (Visit 1-4a), if it is determined a subject did not in fact meet eligibility criteria, the subject may be brought back at a later date to re-attempt the screening process.

Subjects can be re-screened a maximum of three times.

CLN-Protocol-0052 Rev 002: 29-October 2019

#### 7.2. Screen Failures

A screen-fail will be defined as screened subjects who do not meet the inclusion/exclusion criteria prior to randomization at Visit 4b (Day 1).

# 7.3. Subject Withdrawal

Subjects may be discontinued prior to their completion of the study due to:

- adverse events
- protocol violations
- administrative reasons (eg, inability to continue, lost to follow up)
- sponsor termination of study
- other

Note: In addition, any subject may be discontinued for any sound medical reason.

Notification of a subject discontinuation and the reason for discontinuation will be made to Ora and/or study sponsor and will be clearly documented on the eCRF.

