# 8.14. Early Discontinued Subjects

Subjects may voluntarily withdraw from the study at any time. Subjects who withdraw consent or are withdrawn per investigator discretion will be considered early discontinued subjects and should complete the exit visit assessments required at Visit 9.

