#### 8.15. Unscheduled Visits

For unscheduled visits, the reason for the visit should be clearly documented on the appropriate eCRF, including findings from all evaluations that are completed.

These visits may be performed in order to ensure subject safety. All information gathered at unscheduled visits should be recorded on the Unscheduled Visit pages of the source document and corresponding eCRF for randomized subjects.

Evaluations that may be conducted at an Unscheduled Visit (as appropriate, depending on the reason for the visit), include:

- Assessment of Adverse Events
- Assessment of Concomitant Medications
- Best Corrected Visual Acuity (BCVA) using an ETDRS chart
- Urine Pregnancy Test (for females of childbearing potential)
- Slit lamp Biomicroscopy including punctum examination

CLN-Protocol-0052 Page **34** of **61** 

- Visualization of Intracanalicular Inserts
- IOP Measurement
- Dilated Fundoscopy

If a randomized subject does not attend their scheduled visit, eCRF pages for missed visits will be skipped. All efforts should be made to schedule the subject for an Exit Visit (Visit 9) to complete exit procedures.

Inserts that are no longer present or removed at any point in the study will not be replaced.

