### **10.1.** Study Populations

### 10.1.1. Intent-to-Treat Population

The Intent-to-Treat (ITT) population consists of all subjects who are randomized. All data will be included and no subjects will be excluded because of protocol violations. The ITT population will be analyzed as randomized and will be used for the efficacy analyses.

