7.2 Per Protocol

The Per-Protocol (PP) population is a subset of the ITT population and includes the subjects who completed the study through Visit 6b (Day 8; 7 days post-insertion; 8 hours from Visit 6a) with no major protocol violations that would impact the efficacy of the drug. Protocol deviations will be assessed and decisions regarding subject evaluability will be made prior to database lock and unmasking. This population will be analyzed as treated using observed data only for confirmatory analyses.

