8.5 Adjustments for Multiplicity

All six sets of hypotheses described in Section 2.5 will be tested in a hierarchical order, testing the primary hypotheses first (corresponding to Visit 6b), and then proceeding with the key secondary efficacy hypotheses in the order presented below.

- 1. Visit 6b
- 2. Visit 6a
- 3. Visit 5
- 4. Visit 8b
- 5. Visit 8a
- 6. Visit 7

If at any point in the hierarchical order, statistical significance is not demonstrated, testing will stop, and the remaining tests will be deemed not statistically significant.

There will be no adjustment necessary for testing multiple time points within a visit, as statistical significance at all three post-CAC time points is required for a visit to be deemed statistically significant.

9. Disposition of Subjects

Analysis populations, study completion, and withdrawal from the study will be summarized for the ITT population. The summary table will include the numbers of subjects randomized and included in the analysis populations by randomized treatment group for the ITT population and by actual treatment group for the PP and Safety populations. The summary table will also include the numbers of subjects who completed the study. The reasons for withdrawal will be summarized for the applicable subjects. Reasons for withdrawal will include AE, protocol deviation, lost to follow-up, consent withdrawn, Sponsor termination of study, Investigator decision, unsuccessful insertion, other.

Disposition data for all subjects in the ITT population will be presented in a listing. Protocol deviations for the ITT population will also be presented in a listing.

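### Protocol 7.3 allows a randomised subject to be discontinued for a protocol violation, which before Visit 6b turns an analysable deviation into avoidable missing primary data

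*Protocol*

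**What the plan says.** **Exit rule.** Protocol 7.3 states "Subjects may be discontinued prior to their completion of the study due to" a list of reasons, the second being "protocol violations". Adverse events are a separate entry, and a note adds any sound medical reason. The section does not distinguish subjects before and after randomisation, or stopping treatment from leaving the study.

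**What is collected after exit.** Protocol 8.14 says that subjects who withdraw consent, or whom the investigator withdraws, "will be considered early discontinued subjects and should complete the exit visit assessments required at Visit 9". Protocol 8.13 and Appendix A show no challenge and no itching assessment at Visit 9. Protocol 8.15 adds: "If a randomized subject does not attend their scheduled visit, eCRF pages for missed visits will be skipped".

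**Disposition.** SAP Section 9 carries the reason forward: "Reasons for withdrawal will include AE, protocol deviation, lost to follow-up, consent withdrawn".

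**How violators are analysed.** Protocol 10.1.1 and SAP 7.1 define ITT as all randomised subjects: "All data will be included and no subjects will be excluded because of protocol violations". The per-protocol population (Protocol 10.1.2, SAP 7.2) takes those who completed through Visit 6b "with no major protocol violations that would impact the efficacy of the drug". SAP 8.4 keeps out-of-window scheduled visits in the summaries and treats the deviation as possible grounds for per-protocol exclusion only.

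**The concern.** Everywhere except 7.3, the plan treats a violation as a matter for analysis: the subject stays, is scored, and may drop out of the per-protocol set. Requiring both completion of Visit 6b and absence of a major violation makes sense only if some violators complete Visit 6b. Section 7.3 lets a site take the other course and end participation, after which no itching score follows.

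A mistimed visit is the clearest example. SAP Table 1 gives no window for Visits 5 to 8b, so an off-day visit could easily be logged as a deviation. SAP 8.4 would keep its data; 7.3 would permit the subject to be exited instead.

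At stake is missing primary data that arise from a discretionary decision and may be related to response. The roughly 10 extra places for subjects who do not complete Visit 6b can restore the count, but they do not recover the lost subjects' own scores.

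**Working it through.** **1. Does the exit lose the primary score?** The outcome depends on when the exit falls.

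| Time of exit for a violation | Itching scores kept | Visit 6b score |
|---|---|---|
| Before Visit 5 | Visit 4a baseline only | missing |
| After Visit 5 or 6a, before 6b | Visit 4a, plus 5 or 5 and 6a | missing |
| After Visit 6b | includes 6b | present; later key secondary scores missing |

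**2. Does the planned handling restore it?** (Protocol 10.7; SAP 8.2.1 and 12.1)

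- *MCMC (primary):* the model holds treatment, the Visit 4a score and the response, fitted separately for each visit and time point. It uses neither the subject's Visit 5 and 6a scores nor the reason for exit. A subject lost for a response-related reason is imputed as typical of that arm and baseline.
- *LOCF:* carries values only within a visit, so it cannot fill a Visit 6b missed entirely.
- *WCO:* fills only data missing because anti-inflammatory or anti-allergy medication was prescribed. An exit for a mistimed visit falls outside it.
- *BOCF:* fills the gap with the Visit 4a score.
- *Observed data and per-protocol:* the subject contributes nothing at Visit 6b.

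So the primary analysis relies on a missing-at-random model with two predictors, and only one of the three single-imputation analyses clearly supplies a value.

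**3. Planned power, reproduced.** Inputs from Protocol 10.6 and SAP Section 5: 40 per arm, differences of 0.87, 1.08 and 1.13, SD 1.0, two-sided alpha 0.05. For a two-sample t-test with 78 degrees of freedom, the noncentrality is difference / (1.0 × √(2/40)). Power is 97.0%, 99.8% and 99.9%. The product under independence is 0.9701 × 0.9975 × 0.9988 = 0.9665, or 96.7%. The plan's figures are confirmed.

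**4. Power if k subjects per arm have no Visit 6b score.** The documents give no rate, so k is assumed. Column A analyses 40 − k per arm. Column B keeps 40 per arm but gives the k subjects no treatment benefit, so each difference is multiplied by (1 − k/40).

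| k per arm | A: joint power | B: joint power |
|---|---|---|
| 0 | 96.7% | 96.7% |
| 1 | 96.2% | 95.8% |
| 2 | 95.7% | 94.7% |
| 4 | 94.6% | 91.9% |

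**5. Possible shift in an arm mean.** If a share f of an arm is lost and their true scores differ by d from those who remain, filling them in at the remaining subjects' level shifts the arm mean by f × d.

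- Low end: f = 1/40, d = 0.5, giving 0.0125, about 0.01 units.
- High end: f = 4/40, d = 1.0, giving 0.10 units. Against the smallest planned difference this is 0.10 / 0.87 = 11%.

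Both f and d are assumptions. The sign depends on which subjects are exited and from which arm.

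**The case against.** The best case for the plan has several parts.

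- *No conflict with ITT.* A reader might infer that 7.3 contradicts the ITT definition. It does not. That definition governs analysis: it keeps every randomised subject and uses the data that exist, but does not promise scores after an exit. This stands.
- *The loss is not automatic.* A reader might infer that violators' scores are never collected. The rule is permissive, scores taken before exit are kept, and an exit after Visit 6b costs the primary endpoint nothing. This stands.
- *Safety follow-up.* A reader might infer that exit ends it. Protocol 8.14 still asks for the Visit 9 assessments, and 9.4.2 follows ongoing serious events after discontinuation. At most, follow-up is shortened.
- *Other routes lose more.* Sections 7.7 (prescribed medication, safety follow-up only) and 7.8 (one insert present, no further challenge) also produce missing scores. A subject who takes an antihistamine sits close to 7.7, so that case does not isolate the effect of 7.3. This stands, and it limits how far the fix should reach.
- *Missing data are planned for.* True, but step 2 of the working shows that the primary model cannot recover a response-related loss and that LOCF and WCO mostly do not apply.
- *SAP 8.4 already keeps mistimed visits.* It does so once the data exist. It does not stop a site from exiting the subject under 7.3.

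**Conclusion.** The point holds in a limited form. Protocol 7.3 together with 8.14 permits a discretionary exit that replaces a usable Visit 6b score with an imputed one, while the rest of the plan is set up to keep and analyse violators. It is a stated rule with an avoidable cost, not just a missing detail.

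Its size is unknown. On the assumed ranges the arm mean moves by about 0.01 to 0.10 units. The 11% figure takes both upper limits in one arm against the smallest planned effect. Joint power falls from 96.7% to 94.6% with 4 unscored per arm, or to 91.9% if those subjects are counted as having no benefit, so power is not the issue. A reader might infer a bias in favour of the insert, on the reasoning that vehicle subjects have more symptoms and so commit more violations. The documents give no rate by arm, and the direction cannot be established.

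**What to change.** In Protocol 7.3, state that for a randomised subject a protocol violation alone is not a reason to end scheduled efficacy assessments, and that violations are handled through the per-protocol population. Leave exits for an adverse event, a sound medical reason or withdrawal of consent as they are.

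This change concerns data collection only. The sponsor should reconcile it with 7.7 and 7.8, which set when subjects are followed for safety only or are not challenged; the new sentence should not override either section.

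Keep protocol deviation among the withdrawal reasons in SAP Section 9. Deleting it would move any such exits into investigator decision or other and make them harder to see.

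The cost is a sentence or two in 7.3, with a cross-reference to 7.7 and 7.8. No visits are added, because these assessments are already scheduled, and the SAP analyses do not change.

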# 7.4. Product Quality Complaints

All product quality complaints of the OTX-DP or PV will be documented on the appropriate eCRF and reported to Ocular Therapeutix or designee within 24 hours. Ocular Therapeutix will advise whether the investigational product(s) is still suitable for use or, should be returned to the Sponsor for additional analysis and investigation. The product quality complaint will be included in the final analysis.

### 7.5. Treatment of OTX-DP or PV

Qualifying subjects will be randomized at Visit 4b (Day 1) to receive one of the following treatment arms bilaterally:

- OTX-DP (N=40 subjects) or
- PV (N=40 subjects)

In the OTX-DP arm, subjects will receive OTX-DP (dexamethasone, 0.4 mg) until insert absorption or removal (if needed), whichever comes first.

Randomization is at a 1:1 ratio (active:vehicle).

### **7.6.** Concomitant Medications

A concomitant medication is any drug or substance administered from Visit 1 (Screening) through the last study visit, Visit 9 (Day 30). The generic name of the drug or substance, the dose, the route of administration, the duration of treatment (including the start and stop dates), the frequency, the indication, and whether or not the medication was taken due to an AE will be recorded for each drug or substance.

Subjects should be instructed not to start taking any new medications, including nonprescription drugs and herbal preparations, unless they have received permission from the Investigator. The use of any concurrent medication, prescription or over-the-counter (OTC), is to be recorded on the subject's

CLN-Protocol-0052 Page **26** of **61** 

Rev 002: 29-October 2019

source document and corresponding eCRF along with the reason the medication was taken.

Concurrent enrollment in another investigational product study is not permitted.

#### 7.7. **Rescue Therapy**

Cold compress should first be used in the management of allergic symptoms. Subjects may be prescribed anti-inflammatory or anti-allergy medication at the Investigator's discretion. If prescribed such anti-inflammatory or anti-allergy medication, the insert will not be removed and subjects will be followed for safety only.

Currently marketed over-the-counter anti-allergy eye drops (i.e., anti-histamine/ vasoconstrictor combination products such as Visine®-A®) may be administered to subjects at the end of the subject's last visit, after all evaluations are completed.

#### 7.8. Early Loss of Insert and Patient Follow-up

If at any point post-insertion, the subject is experiencing discomfort or an undesirable reaction due to OTX-DP or PV, it may be removed per the instructions in Appendix H, and the subject should be exited (discontinued) at that time.

If only 1 insert is present at any visit prior to a subject's Exit Visit (Visit 9), that subject should continue in the study for safety. These subjects will not undergo the conjunctival allergen challenge and will therefore return for Visit 9. At this visit, the following procedures will be performed:

- Update of Medical/Medication History
- Assessment of Adverse Events
- Best Corrected Visual Acuity (BCVA) using an ETDRS chart
- Slit Lamp Examination, including punctum exam
- Visualization of OTX-DP or PV
- **IOP Measurement**
- Dilated Fundoscopy Examination

Intracanalicular inserts that are no longer present or removed at any point in the study will not be replaced.

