to induce a number of severe and sometimes irreversible side effects, such as osteoporosis, diabetes, Cushing's syndrome, glaucoma, and muscle wasting (Schäcke et al, 2002, Rizzo et al, 2006). For local ocular administration, GCs exhibit a variety of effect/side effect rations, with the primary adverse events (AEs) of concern being elevation of intraocular pressure (IOP), cataract formation, and increased vulnerability to superinfection (Wang et al, 2009, Kersey et al, 2006, Rizzo et al, 2006). All currently marketed ophthalmic steroids carry the warning that use for longer than 14 days should only be carried out under close physician supervision, and it is generally recommended that the dose be tapered slowly over several days (Rizzo et al, 2006).

Dexamethasone, one of the most powerful GCs, is already marketed in the US as a sterile ophthalmic solution for the treatment of "steroid responsive inflammatory conditions of the palpebral and bulbar conjunctiva, cornea, and anterior segment of the globe, such as allergic conjunctivitis...". While dexamethasone and other GCs are presumed to be the most clinically effective in the treatment of late-phase inflammatory allergic reactions, their well known safety limitations for long-term use prohibit wide-spread adoption of this treatment.

Use of the OTX-DP seasonally creates a low, tapered, consistent dose of dexamethasone, possibly minimizing or possibly eliminating negative side effects of general topical ophthalmic GC use, while retaining its anti-inflammatory effects that may be particularly beneficial in the treatment of latephase ocular allergy.

One Phase 2, multicenter, prospective, randomized, double-masked vehicle controlled study in 68 subjects was completed utilizing the modified Ora-CAC® model. The study evaluated the safety and efficacy of OTX-DP as a sustained release drug depot for the treatment of the signs and symptoms of chronic allergic conjunctivitis. At 2 weeks, 4 weeks and 6 weeks after insertion of the OTX-DP, subjects underwent a series of 4 CACs over a period of 48 hours followed by clinical evaluation of the signs and symptoms of chronic allergic conjunctivitis. The co-primary efficacy endpoints were ocular itching and conjunctival redness at 14 days after

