### **OTX-DP** or **PV** Presence by Visual Technique

The Investigator will assess the presence of the insert at Visits 4b, 5, 6a, 6b, 7, 8a, 8b, and 9 by using a slit lamp with a blue light and yellow filter.

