13.4 Intraocular Pressure (IOP)

Intraocular pressure will be assessed post-CAC by contact tonometry in each eye at Visits 2 (Day -5), 6b (Day 8), 8b (Day 15; 8 hours post Visit 8a), 9 (Day 30). The assessment is performed post-CAC for visits when the CAC is administered. Results will be taken from a single measurement and will be recorded in mmHg.

The observed IOP and change from baseline will be summarized using continuous descriptive statistics by visit, treatment group, and eye for the Safety population. The number of instances where IOP \geq 30 mmHg and increases 10 mmHg over baseline will also be summarized using counts and percentages.

A subject listing of IOP will also be produced.

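### Protocol 7.8 names only Visit 9 as the return visit after loss of one insert, which on its most natural reading drops the Day 15 IOP check and, for loss found before Visit 6b, the Day 8 check too

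*Protocol*

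**What the plan says.** Protocol 7.8 covers a subject found with only one insert at any visit before exit. It says "that subject should continue in the study for safety" and then "These subjects will not undergo the conjunctival allergen challenge and will therefore return for Visit 9". A list of procedures follows, introduced by the words 'At this visit'. It includes IOP and dilated fundoscopy. Lost inserts are not replaced.

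Loss can come to light at any post-insertion visit. Appendix G states: "The Investigator will assess the presence of the insert at Visits 4b, 5, 6a, 6b, 7, 8a, 8b, and 9".

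After insertion, IOP is scheduled at Visits 6b, 8b and 9 only (Protocol 8.9, 8.12, 8.13 and Appendix A; SAP 13.4). Visits 5, 6a, 7 and 8a have none. An Appendix A footnote times IOP after the last challenge assessments. SAP 13.4 words the timing conditionally: "The assessment is performed post-CAC for visits when the CAC is administered".

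Extra attendances are optional. Protocol 8.15 says of unscheduled visits: "These visits may be performed in order to ensure subject safety". IOP is among the assessments that may be done at them.

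**The concern.** A subject retained for safety gets fewer safety checks than one who keeps both inserts. The only reason 7.8 gives is that the challenge has stopped, and that is no reason to stop measuring pressure. In an OTX-DP subject the remaining insert may still be releasing dexamethasone. Protocol 4.2 reports effects lasting at least 6 weeks in the Phase 2 study and at least 4 weeks in the first Phase 3 study, so activity past Day 15 is plausible. Placebo subjects follow the same rule because treatment is masked.

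Raised IOP heads the list of adverse events of concern that Protocol 4.2 gives for local ocular steroids. The same section adds: "All currently marketed ophthalmic steroids carry the warning that use for longer than 14 days should only be carried out under close physician supervision". The Day 15 check, 14 days after insertion, is lost in every affected case on the natural reading. The adverse event query, visual acuity and slit-lamp examination at the skipped visits are lost with it.

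**Working it through.** **Inputs.** Insertion is Day 1 and there is no Day 0 (SAP 3.1). Visit 2 is Day -5 or -4, Visit 5 Day 7, Visits 6a and 6b Day 8, Visit 7 Day 14, Visits 8a and 8b Day 15, and Visit 9 Day 30 to 33 (Appendix A). IOP visits are 2, 6b, 8b and 9.

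**The plan's own figures first.** Days since insertion = study day - 1. Visit 6b: 8 - 1 = 7. Visit 8b: 15 - 1 = 14. Visit 9: 30 - 1 = 29 to 33 - 1 = 32. These match the Appendix A row for days after insertion.

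**Planned gaps between IOP readings.**
- Visit 2 to 6b, less one day for the missing Day 0: 8 + 4 - 1 = 11 or 8 + 5 - 1 = 12 days.
- Visit 6b to 8b: 15 - 8 = 7 days.
- Visit 8b to 9: 30 - 15 = 15 to 33 - 15 = 18 days. This is the longest.

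**What 'At this visit' refers to.** Visit 9 is the nearest antecedent. The list also contains dilated fundoscopy, which after insertion is scheduled only at Visit 9. That makes Visit 9 the most natural reading (reading A). The list could instead mean the visit where loss is found (reading B).

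| Loss found at | A: interim IOP dropped | A: resulting interval (days) | B: days from that visit's IOP to Visit 9 |
|---|---|---|---|
| Visit 5 (Day 7) | Day 8 and Day 15 | 29-32, insertion to first IOP | 30-7 to 33-7 = 23-26 |
| Visit 6a (Day 8) | Day 8 and Day 15 | 29-32, insertion to first IOP | 30-8 to 33-8 = 22-25 |
| Visit 6b (Day 8) | Day 15 | 30-8 to 33-8 = 22-25 | 22-25 |
| Visit 7 (Day 14) | Day 15 | 22-25, from Day 8 | 30-14 to 33-14 = 16-19 |
| Visit 8a (Day 15) | Day 15 | 22-25, from Day 8 | 30-15 to 33-15 = 15-18 |
| Visit 8b (Day 15) | none | 15-18 | 15-18 |

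For loss found at Visit 5 or 6a under reading A, the interval between consecutive readings runs from the Visit 2 baseline: 30 + 4 - 1 = 33 to 33 + 5 - 1 = 37 days.

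The Visit 6b and 8b rows count that visit's own IOP as done. Section 7.8 stops only the challenge, 8.9 and 8.12 list IOP as a separate item, and the SAP's post-challenge timing applies only where a challenge is given.

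**How many subjects.** The documents give no insert-loss rate. On an assumed 1% to 10% of 40 OTX-DP subjects, 0.01 x 40 = 0.4 to 0.10 x 40 = 4 would be affected. Protocol 4.2 gives 6% with increased IOP in the cataract-surgery studies, an imperfect comparator. Multiplying gives 0.4 x 0.06 = 0.024 to 4 x 0.06 = 0.24 IOP events. That counts every IOP event in such subjects. Events missed or found late because of 7.8 could, on these assumptions, be no more than that.

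**The case against.** **The list may not mean Visit 9.** It omits items that Protocol 8.13 has at Visit 9: the pregnancy test, insert removal, the relief drop and study exit. As a description of Visit 9 it is an incomplete duplicate; as a work-up when loss is found it has a purpose. This stands as a real ambiguity. It removes the concern for Visit 8a and leaves one extra day for Visit 7, but not for Visits 5 to 6b.

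**The general schedule has no exemption.** Appendix A, 8.9 and 8.12 list IOP for everyone, so a site could still do it. It could, but 7.8 is the specific rule, and its 'therefore' makes going to Visit 9 the consequence of stopping the challenge. Unscheduled visits are discretionary.

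**The two-week warning fits loosely.** It concerns use beyond 14 days, and Visit 8b falls at exactly 14. Past that point every subject has only Visit 9. For loss found at Visits 6b to 8a, reading A lengthens the gap by 22 - 15 = 7 days. All of this stands and limits the weight of the point.

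**Stronger inferences that the documents do not support.** A reader might infer that loss noticed at Visit 4b is the worst case. That is doubtful: Appendix G allows repositioning, and a new insert if the first hydrates too early. SAP section 9 also lists unsuccessful insertion as a withdrawal reason, so a failed insertion may never reach the 7.8 route. A reader might also infer that these subjects go unmonitored. They do not: Visit 9 still measures IOP. Entry excludes glaucoma, IOP above 22 mmHg and previous steroid-related IOP rises, and Protocol 4.2 expects a low, tapered dose.

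**Conclusion.** The point holds as a modest gap in safety follow-up. Loss found at Visits 5 to 6b lengthens the wait for IOP under both readings of the list: to 29-32 days from insertion (Visits 5 and 6a) or 22-25 days from Day 8 (Visit 6b) on the natural one, and to 22-26 days on the other. Loss found at Visit 7 or 8a matters only on the natural reading, and loss found at Visit 8b not at all. These figures assume nominal visit days and that sites follow 7.8 as the specific rule.

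It would be too strong to say that the Day 8 and Day 15 checks are certainly lost, because the wording is open, or to read the event arithmetic as harm caused by the rule. The number affected cannot be known from the documents and the expected effect is small. The primary endpoint, alpha and power are unaffected. This is a cheap improvement to consider.

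**What to change.** Add two or three sentences to Protocol 7.8:

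- One-insert subjects skip only the challenge and its scoring. At the visit where loss is found they have IOP and the other safety procedures.
- They attend any remaining Visit 6b (Day 8) and Visit 8b (Day 15) for adverse event query, visual acuity, slit lamp with punctum exam, insert visualisation and IOP, and then Visit 9.
- An IOP taken at Visit 6a or 8a counts as that day's reading, so nobody returns eight hours later for it alone.
- The list after 'At this visit' applies to Visit 9.

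The longest gap after insertion then returns to 15-18 days, as for everyone else. Apart from the IOP when loss is found, the visits and procedures are already in Appendix A. The cost is two short attendances if loss is found at Visit 5, one if at Visit 6a, 6b or 7, and none if at Visit 8a or 8b.
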